(i) Fidelity assessed according to a fidelity checklist (developed in collaboration with the delivery team, prior to the internal pilot – see later in Process Evaluation) (green= ≥ 80 of sessions meet criteria; amber=50-79%; red=<50%);

(ii) Adherence: session attendance (green= $\geq 75\%$ of families attend at least the first 8 of the 10 sessions; amber= 50-74%; red=<50%).

Outcomes

(i) Data completeness for the Strengths and Difficulties Questionnaire (SDQ) parent reported young person externalising problems score at baseline: green= $\geq 75\%$; amber=50-74%; red=<50%.

The final progression criterion will be an assessment to confirm that the support in the intervention arm is sufficiently different to the control arm. This will be an assessment based primarily on a SAU survey.

Information from the SAU survey will be examined for any overlap with the content of the TEEN TRIPLE P intervention.

Design

A two-arm cluster (with families as the clusters) randomised efficacy RCT of Standard Teen Triple P (TEEN TRIPLE P) plus SAU vs. SAU alone, running over 40 months, involving parents and foster carers of young people aged 11-15 years on the edge-of-care. There will be a 6- and 12-month follow-ups, and a process evaluation and internal pilot.

Procedure

Parents and foster carers identified by case-holding social workers and edge-of-care teams across six local authorities (Cambridgeshire, Peterborough, Birmingham, London Borough Merton, Gloucestershire, and Wirral). Participants (primary parents/carers) will be screened by case-holding social workers and edge of care teams to check initial eligibility. Those who are likely to be eligible will be invited to take part in the trial.

All participants who agree to participate and for whom consent has been given will be screened to ensure they meet the eligibility criteria. Consent from those with parental responsibility is required, and young person assent when under 16 years of age – for research participation by young people. If the local authority has parental responsibility, then the social worker would consent to the inclusion of the young person on behalf of the local authority.

Baseline assessments will be completed prior to randomisation. Families randomised to the intervention arm will receive TEEN TRIPLE P as well as existing edge-of-care services (SAU), and those randomised to the control arm will receive SAU alone.

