We will also consider in a sensitivity analysis the role of Triple P practitioner as an additional source of clustering. As practitioners will deliver the intervention to several families allocated to the intervention arm only, this will be a form of partial nesting and may lead to an underestimation of standard errors (and thus inflated Type-I error) if not appropriately accounted for. To account for any clustering, we will fit a heteroscedastic partially nested mixed-effects model. We will also report intra-cluster correlation coefficients, the number of clusters, and cluster sizes.

Secondary outcomes will be analysed similarly. However, secondary outcomes that are adolescent self-report will use linear regression to compare mean scores between trial arms, controlling for baseline scores, age, sex, and local authority. No random effects are included when analysing these outcomes as we do not need to adjust for parent clustering of responses, i.e. there is no dependency of responses from within the same household as we only anticipate one adolescent per household to respond.

We will explore the extent to which there were differential intervention effects by local authority by extending our primary analysis model to include sub-group by trial arm interaction

terms. Similarly, potential moderators, young person learning disability status, ethnicity, and in-care vs in family home status, will be explored by inclusion of an interaction of moderator and treatment allocation variables into the primary analysis model. In addition to interpreting the magnitude and statistical significance of interactions, plots of the interactions will also be examined. These analyses will be hypothesis generating in nature only (i.e., will not be confirmatory and only indicate whether further research targeting the intervention may be warranted).

We will conduct two further sensitivity analyses:

- Exploring the impact of missing data on trial outcomes by investigating likely missing data mechanisms and re-fitting the primary outcome within a multiple imputation framework (including exploring MAR and MNAR mechanisms via delta-based controlled multiple imputation);

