- Exploring the impact of different levels of intervention receipt (adherence) and fidelity of intervention delivery on outcomes. We will use either two-stage least squares instrumental variables regression or inverse probability of treatment weighting methods to examine the effect of the intervention in those who receive varying levels of it.

All analyses will be checked subject to satisfying required assumptions. These checks include:

1. Linearity – plotting residuals vs predictor(s). If a structure is present, then transformation or an alternate model specification is required (i.e. GLM).
2. Homogeneity of variance – variance of the residuals across groups is the same. There is scope to fit models allowing for heterogeneous groups, but the setup is different (Generalized linear mixed model - GLMM).
3. Residuals are approximately normally distributed – plotting QQ plot

If distributional assumptions are not satisfied, as appropriate, a generalized linear model with alternate link function will be used. Alternatively, data transformation could be used but use of the GLM is preferable.

Longitudinal follow-ups (12 months post-randomisation)

We will fit linear mixed models, accounting for repeated post-randomisation measures (6- and 12-months post-randomisation) within participants, adjusting for baseline measures, adolescent factors (age, gender, parents in household), local authority and practitioners to investigate the overall effect of the intervention on post-randomisation measures.

Exploratory mediation analyses may also be carried out to examine variables at 6 months that may mediate intervention effects between baseline and 12-month follow-up. Any such analyses will be specified once a final Logic Model is confirmed. We would, however, anticipate

a theoretically derived set of questions relating to changes in parenting practices to mediate the impact of intervention on SDQ outcomes.

Analyses described in this section will be reported in the 12-month post-randomisation report only.

Withdrawal & participant retention

Withdrawal

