We may lose participants from the trial (i.e., non-completion of measures over time). We will: (i) offer participants shopping vouchers for taking part in this trial, contingent upon questionnaire completion at each timepoint, and stepping this to encourage completion at the follow-up timepoints (baseline=£10, 6-months=£20, 12-months=£25). Adolescents and family carers will also be offered £20 shopping vouchers for participating in an interview, and (ii) send adolescents and their families thank-you cards following each contact.

Difficulties with literacy/other social inequalities

Some participants may have difficulties with reading and writing. We will make materials available in alternative formats (e.g., telephone completion, audio file, video, EasyRead) and provide a choice of data completion methods (see earlier).

Contamination

There may be a risk of contamination in this trial, if the same practitioners will be supporting parents/ carers and adolescents in both trial arms. However, the delivery team have assured us that this will not be the case. Different practitioners will be allocated to each condition, dependant on their training in TEEN TRIPLE P. Other parenting interventions may also be delivered to the SAU only group following recruitment. The internal pilot will provide data to check on these issues.

COVID-19

In the event of continued pandemic-related disruption, research processes can be moved entirely to non-contact methods (and we already plan to use a variety of data collection methods – see earlier). Thus, if intervention delivery can continue, the trial could continue in a situation where restrictions are re-introduced. The statistical analysis plan will also include strategies to evaluate any effects of pre- vs. during/post-pandemic restriction data collection.

Timeline

Start Date	End date	Activity	Staff responsible/ leading
		Project and Evaluation Set Up and Mobilisation stage - Pilot	

03/01/23	31/01/23	Recruitment of local site coordinators. Implementation Planning (Consultant weekly meetings with each of the sites coordinators, preparing for the trial) & Managers briefings	Project Team
01/02/2023	28/02/2023	Evaluator completes protocol	Evaluator
01/03/2023	15/03/2023	YEF to review protocol and provide feedback. In some cases an external peer reviewer will also provide feedback. (including reviewing progression criteria)	YEF, Project team, Evaluator

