15/03/2023	15/04/2023	Evaluator incorporates feedback and submits final protocol	Evaluator
01/02/2023	30/04/2023	Evaluator drafts information sheets and privacy notices	Evaluator
01/02/2023	30/04/2023	Evaluator incorporates feedback and submits final information sheets and privacy notices	Evaluator
01/02/2023	30/04/2023	Evaluator prepares ethical application and obtains approval /provides confirmation to YEF	Evaluator
01/02/2023	15/04/2023	Project team agree Information Sharing Agreements (ISAs) and referral mechanism with partners/stakeholders	Project team, Evaluator
01/02/2023	30/04/2023	Recruitment of evaluation team (Research Fellow)	Evaluator
17/04/2023	17/06/2023	Recruitment of evaluation team (Research Assistant)	Evaluator
16/01/2023	15/03/2023	Recruitment, vetting and DBS checks of practitioners (LAS responsibility) for project intervention delivery and site management	Project team
01/05/2023	01/07/2023	Research staff training	Evaluator
17/04/2023	17/07/2023	Practitioner briefings, Practitioner training, accreditation and 1/2 day clinical workshops = 120 practitioners across 6 sites	Project team
01/02/2023	30/04/2023	Recruit PAG members	Evaluator, Project team

01/02/2023	31/03/2023	Finalise information sharing agreements	Evaluator, Project team, YEF
01/04/2023	30/06/2023	Building and testing database	Evaluator
19/06/2023	31/07/2023	Site initiation visits	Evaluator
01/04/2023	31/07/2023	Statistical analysis plan	Evaluator
		Project and Evaluation Delivery - Pilot	
01/08/2023	28/02/2024	Start recruitment and eligibility assessments	Project team, Evaluator
21/08/2023	23/03/2024	Delivery of intervention	Project team
01/11/2023	30/11/2023	Trainer Facilitated Clinical support workshops (1 per site over the pilot)	Project Team
01/06/2023	31/08/2023	Survey of SAU	Evaluator
01/08/2023	28/02/2024	Baseline data collection	Evaluator
01/08/2023	28/02/2024	Randomisation	Evaluator
01/02/2024	31/08/2024	6 month Follow up data collection	Evaluator
01/08/2024	28/02/2025	12 month Follow up data collection	Evaluator
01/03/2024	30/04/2024	Submission of draft pilot report	Project team, Evaluator
01/04/2024	30/04/2024	YEF make decision whether to progress to efficacy trial	YEF
15/04/2024	15/07/2024	Submission of final peer-reviewed pilot report	Project team, Evaluator

01/01/2024	01/02/2024	Pilot phase review - lessons learned	Evaluator, Project team, YEF
		Project and Evaluation Delivery - Efficacy	

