Following creation of the imputed datasets, the corresponding total scores will be calculated using the imputed item level data. All imputed datasets will then fit the primary and secondary models and pool estimates following Rubin's rules (Rubin, 2004; van Buuren, 2018).

Primary outcome

Given that each item is an ordered category, we will use an ordinal regression within the imputation model for each item.

Secondary outcome Similarly, the correct link function will be used according to the item's structure for each of the secondary outcomes, i.e. binary or ordered categorical accordingly. Therefore, a logistic or ordinal model will be used in the imputation for these items.

Additional analyses

Longitudinal followup analyses (12 month only) – Primary outcome

We will fit linear mixed models, accounting for repeated post-randomisation measures (6- and 12-months post-randomisation) within participants, adjusting for local authority to investigate the overall effect of the intervention on post-randomisation measures.

$$L1: Y_{ijk} = \beta_{0jk} + \beta_{1jk}time_{ijk} + r_{ijk}, \quad r_{ijk} \sim N(0, \sigma^2_{|X})$$

$$L2: \beta_{0jk} = \gamma_{00k} + \mu_{0jk}, \quad \mu_{0jk} \sim N(0, \tau_2^2)$$

$$\beta_{1jk} = \gamma_{100} + \mu_{1jk}, \quad \mu_{1jk} \sim N(0, \tau_2^2)$$

$$L3: \gamma_{00k} = \delta_{000} + \delta_{001}local_authority_k + \delta_{001}TX_k + \varsigma_{0k}, \quad \varsigma_{0k} \sim N(0, \tau_3^2)$$

Longitudinal followup analyses (12 month only) - Secondary outcomes

Secondary outcomes will be analysed similarly, but

$$L1: g(Y_{ijk}) = \beta_{0jk} + \beta_{1jk}time_{ijk} + r_{ijk}, \quad r_{ijk} \sim N(0, \sigma^2_{|X})$$

$$L2: \beta_{0jk} = \gamma_{00k} + \mu_{0jk}, \quad \mu_{0jk} \sim N(0, \tau_2^2)$$

$$\beta_{1jk} = \gamma_{100} + \mu_{1jk}, \quad \mu_{1jk} \sim N(0, \tau_2^2)$$

$$L3: \gamma_{00k} = \delta_{000} + \delta_{001}local_authority_k + \delta_{001}TX_k + \varsigma_{0k}, \quad \varsigma_{0k} \sim N(0, \tau_3^2)$$

For the remaining secondary outcomes, their effect sizes will be reported as either Hedges' g (same as primary outcome) or rate ratios (other secondary outcomes, exponentiated parameter estimates), given that generalized linear mixed effects models with log link function are used to model the data and that the measures are positively scored integers with some amount of skew anticipated (Barnett and Dobson, 2008).

Mediation analyses (12 months report only)

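### The protocol's longitudinal model adjusts for practitioners, who serve one arm only, without saying how they enter; the SAP writes a different model

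*Protocol*

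**What the plan says.** Three places in the protocol fix the relation between practitioner and arm.

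- Impact evaluation, Procedure: intervention families receive Teen Triple P on top of usual support, "and those randomised to the control arm will receive SAU alone".
- Analysis of primary and secondary outcomes: "As practitioners will deliver the intervention to several families allocated to the intervention arm only, this will be a form of partial nesting". The protocol answers this with a heteroscedastic partially nested mixed model, as a sensitivity analysis on the 6-month primary outcome.
- Risks, Contamination: "Different practitioners will be allocated to each condition, dependant on their training in TEEN TRIPLE P".

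The protocol section on longitudinal follow-ups then describes a linear mixed model for the 6- and 12-month measures. It adjusts for baseline measures, "adolescent factors (age, gender, parents in household), local authority and practitioners to investigate the overall effect of the intervention on post-randomisation measures". Practitioners stand in the same list as the ordinary covariates. The section does not say whether they are fixed or random, does not say how controls are coded, and does not refer back to the partially nested model.

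The SAP section on longitudinal follow-up of the primary outcome has the same purpose, but the model is "adjusting for local authority to investigate the overall effect of the intervention on post-randomisation measures". Its equations contain time, local authority, arm and random effects. They contain no practitioner, baseline or adolescent term. In the SAP, practitioner appears only as a level-3 random intercept in a 6-month sensitivity analysis, where the coding of controls is again not stated.

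**The concern.** Practitioner is nested in arm. A variable that is present only in the intervention arm, and that identifies that arm completely, cannot be adjusted for like age or local authority. Depending on how it enters, the arm coefficient is undefined, takes on a meaning set by the coding, acquires a standard error that is much too large, or is barely affected. The protocol does not choose among these.

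At stake is the longitudinal estimate of the overall intervention effect, which informs the 12-month parts of secondary objective 2. The 6-month primary analysis is not involved.

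The SAP does not settle the matter by omitting practitioners. It also omits covariates that the protocol promises. An analyst who restores those by copying the protocol's list would bring practitioners in with them.

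**Working it through.** **Inputs.** From the sample size sections: effect 0.35 SD, 90% power, two-sided alpha 0.05, 1.5 parents per family, family ICC 0.5, baseline-follow-up correlation 0.5, 20% of families lost. From the protocol Timeline: 120 practitioners trained. Not in the documents and therefore assumed: practitioner variance *v* (total SD = 1), 0.01-0.10; caseload, 1-5 families per practitioner.

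**1. The plan's own figure.** A t-test needs 172.5, so 173, per arm. Then 173 × (1 − 0.5²) × (1 + 0.5 × 0.5) = 162.2 parents; / 1.5 = 108.1, so 109 families; / 0.8 = 136.25, so 137 families; × 1.5 = 205.5, so 206 per arm and 412 in all. This reproduces the stated size.

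**2. No practitioner term.** Retained families per arm: 137 × 0.8 = 109.6, about 110, taken as 55 with one parent and 55 with two. Residual variance after baseline is 0.75. The family mean has variance 0.75 (one parent) or 0.75 × (1 + 0.5)/2 = 0.5625 (two). Information per arm = 55/0.75 + 55/0.5625 = 171.1. SE = √(2/171.1) = 0.108. Power = Φ(0.35/0.108 − 1.96) = 90%.

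**3. Fixed indicators.** Each intervention family has one practitioner and each control has none, so the practitioner indicators sum to the arm indicator. Rank check:

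| Families per practitioner | Columns with arm | Rank |
|---|---|---|
| 1 | 112 | 111 |
| 2 | 57 | 56 |
| 5 | 24 | 23 |

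The matrix is one short at every caseload. If software resolves this by dropping one practitioner column, the arm coefficient compares that practitioner's *c* families with all controls. With 171.1/110 = 1.556 information units per family, SE ≈ √(1/(1.556*c*) + 1/171.1): 0.57 at *c* = 2 and 0.37 at *c* = 5.

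**4. Ordinary random intercept, all controls on one level.** The control arm then carries one whole practitioner effect. With one family per practitioner, SE = √(0.108² + *v*(1 + 1/110)).

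| *v* | SE | Power at 0.35 |
|---|---|---|
| 0.02 | 0.18 | 50% |
| 0.05 | 0.25 | 29% |
| 0.10 | 0.34 | 18% |

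Caseload matters little here: at *v* = 0.10 the SE is 0.336 with one family each and 0.341 with five.

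**5. Partially nested random effect (intervention arm only).** For *v* = 0.01-0.10 and 1-5 families each, SE is 0.109-0.127 and power 90% down to 78%. A 60-replicate REML simulation (*v* = 0.05, three families each, true effect −0.35) agrees:

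| Coding | Mean SE | Mean estimate |
|---|---|---|
| Partially nested | 0.114 | −0.339 |
| One control level | 0.239 | −0.339 |
| No practitioner term | 0.109 | −0.339 |

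The empirical SD of the estimates was about 0.12 under all three. The one-level coding therefore overstates uncertainty; it does not shift the estimate.

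**6. The two longitudinal models side by side.**

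| Term | Protocol | SAP |
|---|---|---|
| Baseline measure | yes | no |
| Adolescent factors | yes | no |
| Local authority | yes | yes |
| Practitioners | yes, form not stated | no |

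**The case against.** A reader might infer that the 12-month treatment effect is not identifiable, or that the 12-month report would have almost no power. The documents do not support that, for four reasons.

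- The SAP's sections on timing and derivation of outcomes have the two-level analysis repeated at 12 months for the addendum report. That model has no practitioner term. The longitudinal model is an additional analysis.
- The protocol leaves the final analysis to the SAP. By the version histories, SAP v1.2 (15/08/2023) postdates protocol v1.4 (11/07/2023), and the SAP's longitudinal model has no practitioner term either.
- The protocol calls its longitudinal model a mixed model, and the same analysis section has already recognised the partial nesting. Carrying that form forward is a natural reading, and step 5 shows that it does little harm.
- A power near 7% can be reached for the fixed reading, but only with reference-cell coding and about 137/120 = 1.1 families per practitioner. The protocol speaks of several families each, and the 120 are those trained, not a stated number delivering. Fixed effects constrained to sum to zero within the intervention arm would leave the arm SE at about 0.11.

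All of this stands, and it removes the claim of certain harm. It does not remove the ambiguity. The protocol confines partial nesting to a sensitivity analysis, its longitudinal section gives practitioners no separate status, and the one practitioner model that the SAP writes out is not in partially nested form. Nor does it explain why the SAP lacks the baseline and adolescent covariates.

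**Conclusion.** The point holds as a specification gap and a disagreement between documents. The protocol lists, as an adjustment variable, a factor that exists in one arm only, and does not say how it enters. Aliasing under a full set of fixed indicators is exact and depends on no assumption. The inflation from 0.11 to 0.18-0.34 SD applies only to a random intercept with controls on one level, and rests on an assumed practitioner ICC of 0.02-0.10. Under a partially nested form the SE stays at 0.109-0.127 SD. All the SEs are for a single follow-up time; a repeated-measures model would change their size but not the aliasing.

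Separately, the protocol and SAP longitudinal models differ in three sets of terms. The primary 6-month analysis and the repeated two-level 12-month analysis are unaffected. It is worth correcting before analysis, but it does not threaten the trial's main result.

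**What to change.** 1. Protocol, longitudinal follow-ups: delete practitioners from the adjustment list.
2. SAP, longitudinal analyses of primary and secondary outcomes: make the text and both sets of equations adjust for the baseline measure, adolescent factors and local authority. State that baseline is a covariate: the SAP's timing section speaks of all three time points in this model, whereas the longitudinal section names only the two follow-ups.
3. Handle practitioner only as a sensitivity analysis, using the partially nested random effect that the protocol already names: practitioner variance in the intervention arm only, with the coding of controls written down. State the same coding for the SAP's existing three-level 6-month sensitivity model.

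The cost is one phrase in the protocol and a revision of the SAP's longitudinal text and equations. No new data, participants or measurements are needed, because baseline scores, age, sex and living arrangements are already collected.
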